It is estimated that up to 150 subjects will be screened to yield approximately 75 subjects who will enter Single-blind Run-in Period to yield approximately 44 subjects who will enter the Double-blind Treatment Period. A sample size of 38 (completers) will have 81% power to detect a treatment difference of bladder pain/discomfort mean scores of 0.5, assuming a standard deviation of differences of 1.4, using a paired t-test with a 10% one-sided significance level. Assuming a 15% dropout rate, a sample size of 44 would be needed.

Treatment Groups and Duration:

V117957 (6-weeks) and Placebo (5-weeks).

Schema:

Phase Period	Pre-randomization			Post-randomization									
	Screening/ washout	Single-blind Run-in		Double-blind Treatment								Single- blind washout	Follow- up
Day	-28 to -16	-15	-1 ^A	1	14	15	28	35	42	49	56	63	70
Clinic Visit	V1		V2		V3		V4		V5		V6	V7	V8
Phone call ^B				P1		P2		P3		P4			
Treatment		Placebo		V117957 or Placebo								Placebo	

^A At visit 1 subject must meet all inclusion/exclusion criteria. At visit 2, if subject has met all randomization eligibility criteria they may be dispensed double-blind study-drug. ^B Phone contact between clinic visits to assess tolerability and review diary/dosing instructions.

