1.4.1. Primary Efficacy Analyses

The baseline, post-baseline and change from baseline for bladder pain/discomfort scores over last 12 hours (morning and night) will be summarized by treatment group using descriptive statistics and presented graphically. Changes from baseline to endpoint in mean bladder pain/discomfort scores will be analyzed by mixed model with treatment, period and sequence as fixed effects, subject within the sequence as a random effect and baseline as a covariate. Comparison of the active treatment to placebo will be tested at the one-sided significance level 0.10 by means of the corresponding contrast. Plots of the least square mean change from baseline and 90% confidence intervals will be produced by treatment group.

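### Do 90% intervals on each treatment's LS mean clash with a one-sided 0.10 test of the difference?

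*Combined protocol and SAP*

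**What the plan says.** Section 1.4.1 (Primary Efficacy Analyses) analyses change from baseline in mean bladder pain/discomfort score with a "mixed model with treatment, period and sequence as fixed effects, subject within the sequence as a random effect and baseline as a covariate". The decision rule follows: "Comparison of the active treatment to placebo will be tested at the one-sided significance level 0.10 by means of the corresponding contrast". The section then closes with graphical output: "Plots of the least square mean change from baseline and 90% confidence intervals will be produced by treatment group".

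The Synopsis (1.1) sizes the trial on the same one-sided scale: "A sample size of 38 (completers) will have 81% power". The planned effect is 0.5 points, the SD of the within-subject differences is taken as 1.4, and the calculation is made "using a paired t-test with a 10% one-sided significance level".

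The visible text of 1.4.1 names no confidence interval for V117957 minus placebo, and it does not say whether the 90% interval is one- or two-sided.

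**The concern.** There appear to be two mismatches between the test and the interval.

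- **Level.** A one-sided 0.10 test corresponds to a two-sided 80% interval, or to a one-sided 90% bound. A conventional two-sided 90% interval corresponds to one-sided 0.05.
- **Quantity.** The test concerns the within-subject difference. The plotted intervals concern each treatment's mean, so they include between-subject variance that drops out of the difference. They are not a guide to how precisely the difference is known.

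If readers took the plotted intervals as the evidence for the treatment effect, a trial that met its criterion could look negative in its own figure. In a small Phase 1b study with a lenient alpha, the size of the effect and its uncertainty matter for what is done next, so the point deserves a check.

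**Working it through.** **Inputs from the Synopsis and 1.4.1:** n = 38 completers, planned difference 0.5, SD of differences 1.4, one-sided alpha 0.10. **Assumed:** the within-subject correlation ρ between treatments, which the documents do not give; range 0 to 0.7.

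**1. The plan's own figure.** SE of the difference = 1.4/√38 = 0.227, with 37 degrees of freedom. The noncentrality is 0.5/0.227 = 2.20. Paired-t power at one-sided 0.10 is 81.5%, against the stated 81%, so the figure reproduces.

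**2. Level.** Smallest observed difference that passes each criterion:

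| Criterion | t (37 df) | t × 0.227 | Power at 0.5 |
|---|---|---|---|
| One-sided 0.10 (two-sided 80% interval excludes zero) | 1.305 | 0.296 | 81.5% |
| One-sided 0.05 (two-sided 90% interval excludes zero) | 1.687 | 0.383 | 69.7% |

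An observed difference between 0.296 and 0.383 would pass the test while a two-sided 90% interval *for the difference* still covered zero. The probability is 81.5% − 69.7% = 11.8% at the planned effect (11.8/81.5 = 14% of positive trials), and 10% − 5% = 5% under the null. Section 1.4.1 plans no such interval, so these are not rates at which planned outputs would conflict.

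**3. Quantity.** With equal variances, SD of differences² = 2 × SD per treatment² × (1 − ρ), so SD per treatment = 1.4/√(2(1 − ρ)). The half-width of a group 90% interval is 1.687 × SD per treatment/√38. Two such intervals separate once the difference exceeds twice that half-width:

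| ρ (assumed) | SD per treatment | Half-width | Intervals separate above | Positive trials with overlap, true effect 0.5 |
|---|---|---|---|---|
| 0 | 0.990 | 0.271 | 0.54 | 46% |
| 0.3 | 1.183 | 0.324 | 0.65 | 66% |
| 0.5 | 1.400 | 0.383 | 0.77 | 83% |
| 0.7 | 1.807 | 0.495 | 0.99 | 97% |

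Overlap beside a positive test would therefore be common. That is a general property of group means in a crossover and says nothing against the contrast. Separation at ρ = 0.5 already corresponds to a one-sided p of about 0.0009, which shows how far non-overlap is from the planned criterion. These are simple t intervals. The planned model adjusts for baseline, which would normally remove some between-subject variance, lower the residual correlation and move the figures towards the top of the table.

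**4. What a reader can recover.** The contrast estimate is the difference between the two LS means, so the plotted values and the tested estimate agree by construction. Given that difference and the one-sided p-value, the SE follows as difference ÷ t. For example, a difference of 0.296 with p = 0.10 gives 0.296/1.305 = 0.227. An interval for the difference at any level follows from there.

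**The case for a change.** The best argument for a change is that calling the plots descriptive makes matters worse: the primary analysis then specifies no interval at all for the treatment effect. Software will print one, but with no level stated in advance, someone could choose 80% or 90% after seeing the data. One sentence would settle it at no cost in data.

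Part of this stands. The visible paragraph does omit an interval for V117957 minus placebo, and a plot of group means is a poor substitute. The available text cannot show that the interval is missing from the whole plan, though: the numbering goes from 1.4.1 to 1.4.3, and 1.3 refers to a statistical analysis plan, although only for exclusions from the analysis sets.

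The argument also does not reach the decision rule. Alpha, sidedness, model and contrast are fixed, so the choice of interval level cannot turn a negative result into a positive one. On the level itself, reasonable statisticians differ. A two-sided 80% interval mirrors the test, while a two-sided 90% interval beside the p-value is a more cautious summary. If the 90% in the plan was meant as a one-sided bound, the level already matches and only the quantity differs.

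**Conclusion.** The observation is correct but does not call for a change. The intervals in 1.4.1 are valid descriptions of each treatment's mean change. They test nothing, so they need not share the test's alpha. They cannot contradict the contrast or show an absence of effect, because they do not estimate the effect; only a misreading of overlap could suggest otherwise.

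The 11.8% figure depends on a two-sided 90% interval for the difference that the plan does not contain. The separation thresholds of 0.54 to 0.99 depend on an assumed correlation of 0 to 0.7, on unadjusted intervals, and on an overlap rule that the plan never states.

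If the plan is followed as written, the one-sided 0.10 test, its 81% power, the sample size and the trial's conclusion are all unaffected. What remains is a small reporting gap. An analyst would fill it from the same contrast by tabulating the LS mean difference with an interval whose level is stated, and by treating the group plots as descriptive.

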1.4.3. Safety Analyses

All safety data (adverse events [AEs], clinical laboratory results, vital signs, physical examinations, electrocardiograms, Columbia-Suicide Severity Rating Scale and Epworth Sleepiness Scale) will be listed for subjects in the enrolled and randomized safety populations.

AEs will be categorized into Preferred Term (PT) and associated System Organ Class (SOC) using the Medical Dictionary for Regulatory Activities (MedDRA). Treatment-emergent AEs (TEAEs) will be defined as AEs that start after or increase in intensity after the first dose of study drug. TEAEs will be summarized by presenting the incidence of AEs for each treatment group by the MedDRA PT, nested within SOC for the randomized safety population. Medical history will be coded to MedDRA terms. Coded medical history terms will be summarized for all subjects in the randomized safety population.

Laboratory evaluations and vital signs will be summarized by treatment and time point for the randomized safety population. Concomitant and prior medications will be coded using the latest version of the World Health Organization Drug Dictionary and presented in tables and listings

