1.1. Synopsis

Protocol Title:

Multicenter, Randomized, Double-blind Placebo-controlled, Crossover Study to Investigate Effects of V117957 in Female Subjects with Interstitial Cystitis/Bladder Pain Syndrome

Brief Title:

Study of V117957 in Interstitial Cystitis/Bladder Pain Syndrome

Rationale:

V117957 is a selective partial agonist of the nociceptin/orphanin-FQ peptide receptor. V117957 inhibits bladder afferents following systemic administration in rats leading to reduction in the frequency of rhythmic bladder contractions without affecting the magnitude of contraction. V117957 had mixed effects in standard models of overactive bladder in rats (spinal cord injury and bladder outlet obstruction) and was anti-nociceptive in a rat model of interstitial cystitis / bladder pain syndrome (intraperitoneal administration of cyclophosphamide). Based on these animal observations, it is hypothesized that V117957 may be effective in treating symptoms of interstitial cystitis and bladder pain syndrome in humans.

Objectives and Endpoints:

Objectives	Endpoints
Primary	
Evaluate effects of V117957 on bladder pain/discomfort in subjects diagnosed with interstitial cystitis/bladder pain syndrome (IC/BPS) compared to placebo	
 • Bladder pain/discomfort score. 
 – Each evening and morning subject will respond to question “Please indicate the worst bladder pain/discomfort you have had overnight/over the day” using an 11-point numeric rating scale.
[REDACTED]	[REDACTED]

Safety	
Assess safety and tolerability of V117957	Adverse events, Clinical laboratory values, Electrocardiograms, Physical examination, Vital signs, Columbia-Suicide Severity Rating Scale (C-SSRS), Epworth Sleepiness Scale (ESS)

Overall Design:

Phase 1b, multicenter, randomized, double-blind, placebo-controlled, crossover study.

Brief Summary:

The purpose of this study is to investigate the effects of oral administration of 1 mg/day V117957 each evening in female subjects with interstitial cystitis/bladder pain syndrome as compared to placebo. The study will consist of a Screening/ Washout Period (up to 2 weeks), Single-blind Placebo Run-in Period (2 weeks), Double-blind Treatment Period (8 weeks), Single-blind Placebo Washout Period (1 week), and Follow-up Period (up to 1 week).

Number of Participants:

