^A visit window is ±3 day. ^B Visit 1, Day -15, is end of Screening/Washout Period and start of the Single-blind Run-in Period. At this visit, a subject that has met all inclusion/exclusion criteria, has stopped current prohibited medications, and completed all study procedures, will be dispensed single-blind study-drug with instruction to ingest first dose that evening 30 minutes before bedtime. ^C ^D Cystoscopy not required for enrollment; however, if available cystoscopy results within last 5 years should be recorded on eCRF. ^E pain assessment to be completed every 12 hours. ^F Item must be completed at the clinic visit on the same day that study drug is dispensed to subject; the

subject will ingest first dose of study drug that evening. ^G [REDACTED] this must be completed at the clinic visit on the same day that study drug is dispensed to subject; the subject will ingest first dose of study drug that evening. ^H

Table 2 Schedule of Assessments: Post-randomization Phase

Period	Double-blind Treatment									Single-blind washout	Follow-up	
	Day -1	1	14	15	28	35	42	49	56			
Day	-1	1	14	15	28	35	42	49	56	63	70	
Clinic visit ^A	V2 ^B		V3		V4		V5		V6	V7/ EOT/ET	V8/ EOS ^C	
Phone call ^D		P1		P2		P3		P4				
Assessment												
Physical exam, brief	See Table 1, V2 Day -1		X		X		X		X	X		
Vital signs			X		X		X		X	X		
Clinical labs (chem/hem/urine)			X		X		X		X	X		
Urine culture test			X		X		X		X	X		
Urine drug screen										X		
Serum pregnancy test										X		
Urine pregnancy test			X		X		X		X			
12-lead ECG			X		X		X		X	X		
Concomitant medications			X	X	X	X	X	X	X	X	X	X
Adverse events			X	X	X	X	X	X	X	X	X	X
ESS			X		X		X		X	X		
C-SSRS			X		X		X		X	X		
[REDACTED]												
Pain Diary assessment			Twice daily, in morning and evening ^E									
Void Diary assessment (includes PPIUS)		During the week prior to each clinic visit (V3, V4, V5, V6, and V7), subject will record micturition time, type, and urgency for each episode for a minimum of 3 and up to 7-days, and will also record urine volume during 2-day weekend (or other timeframe convenient to subject work/life schedule). Note: The urine volume collection is mandatory during the Run-in Period and optional (but encouraged) during Double-blind Treatment period.										
Study drug dosing (diary)		Once daily, in evening.										
Diary/dosing instruction	See Table 1, V2 day -1	X	X	X	X	X	X	X	X			
Dispensing Study Drug		X	X		X		X		X			
Drug accountability			X		X		X		X	X		

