[REDACTED] PPIUS= Patient Perception of Intensity of Urgency Scale; [REDACTED]. V=visit, P=phone.

^A Visit window is ±3 day.

^B Visit 2, Day -1, is end of Single-blind Run-in Period and start of the Double-blind Treatment Period. At visit 2, a subject that has met all inclusion/exclusion criteria, has met all randomization eligibility criteria, and has completed all study procedures, will be dispensed double-blind study-drug with instruction to ingest first dose that evening 30 minutes before bedtime. ^C May be phone call instead of clinic visit if no safety issue identified. ^D Phone contacts to assess tolerability and review diary/dosing instructions. ^E Pain assessment to be completed every 12 hours.

1.3. Study population:

Enrolled population: The group of subjects who sign informed consent.

Randomized safety population: The group of subjects who are randomized and receive at least 1 dose of the study drug and have at least 1 safety assessment.

Full analysis population: The group of subjects who are randomized, receive study drug, and have at least 1 valid efficacy measurement.

Per protocol population: The group of subjects who are included in the full analysis population but excluding those with major protocol deviations and those who do not receive the actual treatment they were randomized to receive.

Subjects and profiles/metrics excluded from the analysis set will be documented in the statistical analysis plan.

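### Section 1.4.3 compares TEAE incidence between treatments with unequal exposure (6 vs 5 weeks, or 6 vs 2 in the double-blind period) and does not say where run-in and washout events count

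*Combined protocol and SAP*

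**What the plan says.** Section 1.4.3 gives one definition for the whole study: "Treatment-emergent AEs (TEAEs) will be defined as AEs that start after or increase in intensity after the first dose of study drug". TEAEs are then tabulated as incidence by treatment group, by preferred term within system organ class, in the randomized safety population. All safety data are also listed by subject.

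The schedule in section 1.2 has two first doses. Under Table 1, footnote B says that at Day -15 a qualifying subject "will be dispensed single-blind study-drug with instruction to ingest first dose that evening 30 minutes before bedtime". Footnote F, also about the run-in visit, says the "subject will ingest first dose of study drug that evening". Under Table 2, footnote B says that at Day -1 the subject "will be dispensed double-blind study-drug with instruction to ingest first dose that evening 30 minutes before bedtime". The randomized safety population in section 1.3 is "The group of subjects who are randomized and receive at least 1 dose of the study drug and have at least 1 safety assessment"; it does not say which dose.

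The synopsis lists the dosed periods as "Single-blind Placebo Run-in Period (2 weeks), Double-blind Treatment Period (8 weeks), Single-blind Placebo Washout Period (1 week"), followed by up to one week of follow-up. Under Treatment Groups and Duration it gives 6 weeks for V117957 and 5 for placebo. Adverse events are recorded in the run-in, at every post-randomisation visit and call from Day 1 or Day 14 onwards, in the washout and at follow-up.

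**The concern.** In a crossover most subjects contribute to both treatment columns, so a table by treatment needs two rules: which events count, and which treatment each one belongs to. The visible text gives only the first, and its anchor can be read as Day -15 or Day -1.

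The comparison also sets a longer exposure against a shorter one. Incidence grows with time at risk, so the columns can differ when the drug does nothing. If run-in and washout events are pooled into placebo, exposure is closer to balanced, but the column then mixes randomised with non-randomised, single-blind weeks. If they are left out, the exposure ratio becomes 3 to 1. Two programmers could follow section 1.4.3 faithfully and produce different tables.

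Safety and tolerability is a stated objective, and this is the only visible summary of adverse events by treatment.

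**Working it through.** **Step 1: reproduce the stated exposure.** Inputs, all from the synopsis: run-in 2 weeks, double-blind 8, washout 1; V117957 6 weeks, placebo 5.

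- Dosed weeks by period: 2 + 8 + 1 = 11. By treatment: 6 + 5 = 11. They agree.
- Single-blind placebo: 2 + 1 = 3 weeks.
- Double-blind placebo: 5 − 3 = 2 weeks. Double-blind V117957: 8 − 2 = 6 weeks.

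This split is derived, not stated. It takes the durations to apply to every subject; the sequences are not shown. If all 44 subjects take both treatments, planned double-blind exposure is 44 × 6 = 264 versus 44 × 2 = 88 person-weeks; with single-blind weeks pooled, placebo has 44 × 5 = 220.

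**Step 2: constant event rate, no drug effect.** The documents give no adverse event rates, so the weekly rate r is an assumption. Incidence over w weeks = 1 − exp(−r·w).

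| r per week | 6 weeks | 5 weeks | 2 weeks | ratio 6:5 (pooled) | ratio 6:2 (double-blind only) |
|---|---|---|---|---|---|
| 0.02 | 0.113 | 0.095 | 0.039 | 1.19 | 2.88 |
| 0.05 | 0.259 | 0.221 | 0.095 | 1.17 | 2.72 |
| 0.10 | 0.451 | 0.393 | 0.181 | 1.15 | 2.49 |

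At r = 0.05 and 44 subjects, the expected numbers with an event are 11.4 on V117957 against 9.7 (pooled) or 4.2 (double-blind only). A rate per person-week would give a ratio of 1 in both cases.

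**Step 3: events cluster early, no drug effect.** Let the rate halve every h weeks, with the clock restarting at each change of treatment and the six V117957 weeks contiguous (assumed). Fix the 2-week cumulative hazard at 0.10, an incidence of 0.0952. Then H(w) = 0.10 × (1 − 2^(−w/h)) / (1 − 2^(−2/h)), and incidence = 1 − exp(−H).

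- V117957: H(6).
- Double-blind placebo only: H(2).
- Pooled, double-blind placebo first: run-in and double-blind placebo run on for 4 weeks, then one washout week after V117957, so H(4) + H(1).
- Pooled, double-blind placebo last: 2 run-in weeks, then 2 + 1 weeks after V117957, so H(2) + H(3).

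| h (weeks) | V117957 incidence | ratio to 2 weeks | pooled incidence, placebo first | ratio | pooled incidence, placebo last | ratio |
|---|---|---|---|---|---|---|
| 4 | 0.1981 | 2.08 | 0.2015 | 0.98 | 0.2121 | 0.93 |
| 2 | 0.1605 | 1.69 | 0.1883 | 0.85 | 0.2049 | 0.78 |
| 1 | 0.1230 | 1.29 | 0.1744 | 0.71 | 0.1948 | 0.63 |

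If every event falls in the first 2 weeks after a start, the 6:2 ratio is 1.00. The pooled ratio is below 1 because placebo is started twice and V117957 once.

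The fall in the 6:2 ratio needs the two double-blind placebo weeks to begin a new clock. If they merely continue the run-in placebo, their hazard is H(4) − H(2); at h = 4 that is 0.1707 − 0.1000 = 0.0707, incidence 0.0683, and the ratio is 0.1981 / 0.0683 = 2.90.

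**The case against.** The strongest reply is that the visible text is a synopsis with redactions, and that section 1.3 defers some analysis-set detail to the statistical analysis plan. An assignment rule or exposure table could sit in text not shown. That stands, and the point is limited to what section 1.4.3 visibly says.

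A second reply is that a TEAE definition is only an entry rule. Starting it at Day -15 captures more events and need not bias anything if each event is then assigned by treatment at onset. A table by treatment group in a crossover already implies some assignment. This also stands. A reader might infer that the single anchor is itself an error, but the documents do not support that. The Day -1 wording and the randomized safety population make a post-randomisation anchor plausible, though neither states it.

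Third, the synopsis counts run-in and washout weeks in its 5 placebo weeks, so the pooled reading has some support, and there the constant-rate ratio is only 1.17. The 2.72 arises only if those weeks are excluded, which no section states. Leaving them out while keeping incidence alone would worsen the exposure imbalance. That is correct, and it is why separating the weeks must come with exposure-adjusted rates.

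Finally, this is a Phase 1b study of about 44 randomised subjects with descriptive adverse event tables and full listings. That limits the importance of the point. It does not settle how the table is to be built.

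**Conclusion.** The point holds as a cheap improvement to descriptive safety reporting. Efficacy, power and sample size are untouched. On the visible text, the TEAE comparison sets 6 weeks of V117957 against either 5 weeks of placebo that include 3 non-randomised weeks, or 2 weeks of double-blind placebo. With no drug effect, the illustrative ratio is anywhere from 2.72 (constant 5% per week, double-blind only) through 1.17 (same rate, pooled) to 0.63 (pooled, rate halving weekly, placebo last).

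The week counts rest on the stated durations applying to every subject. The ratios rest on assumed rates and shapes, and show sensitivity, not expected results.

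A reader might infer that the table must make V117957 look worse. The documents do not support that, because the direction depends on unstated handling and on event timing. Nor do they show that a drug effect would be hidden; that would need a further mechanism, such as event timing or carryover, which they do not establish.

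**What to change.** In section 1.4.3, state that:

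1. The treatment comparison counts adverse events that start or worsen after the first double-blind dose. Each is assigned to the treatment being taken at onset or worsening, with subjects dosed with that treatment as denominator. An event ongoing at a switch counts for the new treatment only if it worsens.
2. Run-in, washout and follow-up events are shown in separate columns and not pooled with double-blind placebo.
3. Each column header gives exposure, and exposure-adjusted rates stand beside incidence.

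Optional additions are splitting washout and follow-up by last double-blind treatment, and flagging onset soon after a switch from V117957 to placebo, with a window that the sponsor sets before unblinding. The flag would show possible carryover without removing it.

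The cost is wording, a few columns and some programming. The schedule already has a daily dosing diary and adverse event recording, but the case report form is not shown, so the sponsor should confirm that dates of worsening are captured. The downside of person-time rates is that they dilute events that cluster early. In an assumed example, 20 of 100 subjects on drug, all in the first 2 of 6 weeks, give 20/600 = 0.033 per week, while 10 of 100 on placebo over 2 weeks give 10/200 = 0.050. Incidence should therefore stay in the table. If a rule already exists elsewhere, a cross-reference in section 1.4.3 is enough.

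### ESS, ECG and C-SSRS are named safety endpoints, but section 1.4.3 states no by-treatment summary for them, and laboratory values and vital signs get no within-subject difference although each woman takes both treatments

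*Combined protocol and SAP*

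**What the plan says.** The safety objective in the Synopsis (section 1.1) is to assess safety and tolerability. Its endpoints are adverse events, laboratory values, ECG, physical examination, vital signs, C-SSRS and ESS. Table 1 schedules ESS, ECG and C-SSRS at Day -15 and Day -1, and Table 2 schedules them at V3, V4, V5, V6 and V7.

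Section 1.4.3 opens by saying that the safety data, ending with "electrocardiograms, Columbia-Suicide Severity Rating Scale and Epworth Sleepiness Scale) will be listed for subjects in the enrolled and randomized safety populations". It then names what will be tabulated:

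- Adverse events: "TEAEs will be summarized by presenting the incidence of AEs for each treatment group by the MedDRA PT, nested within SOC".
- Laboratory values and vital signs: "Laboratory evaluations and vital signs will be summarized by treatment and time point for the randomized safety population".
- Medical history and medications are coded and tabulated.

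No table, change score or comparison is stated for ESS, ECG, C-SSRS or physical examination.

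The design is a "Phase 1b, multicenter, randomized, double-blind, placebo-controlled, crossover study". The only contrast that uses that structure is in section 1.4.1, where change in bladder pain/discomfort is "analyzed by mixed model with treatment, period and sequence as fixed effects, subject within the sequence as a random effect", with baseline as a covariate.

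**The concern.** Section 1.4.3 names ESS, ECG and C-SSRS in its listing sentence and leaves them out of its summary sentences. A listing lets a reader look up one woman's values. It does not show whether sleepiness or an ECG interval differs between V117957 and placebo. The gap is plainest for ESS, a numeric score collected at seven scheduled points for a drug taken each evening.

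For laboratory values and vital signs a display by treatment is planned, but it does not use the fact that each woman is her own control. Section 1.4.3 also does not say what a time point is, or whether single-blind placebo assessments (V2, V7) share a column with double-blind placebo. A modest shift could go unseen, or a difference between visits could be read as a difference between treatments.

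**Working it through.** **1. Endpoints against planned output** (Synopsis, Tables 1 and 2, section 1.4.3)

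| Endpoint | Scheduled at V3 to V7 | Listed | By-treatment summary stated | Within-subject difference stated |
|---|---|---|---|---|
| Adverse events | yes | yes | yes (incidence) | no |
| Laboratory values | yes | yes | yes, by time point | no |
| Vital signs | yes | yes | yes, by time point | no |
| ECG | yes | yes | no | no |
| C-SSRS | yes | yes | no | no |
| ESS | yes | yes | no | no |
| Physical examination | yes | yes | no | no |

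The data for a comparison are collected. V3 to V6 (Days 14, 28, 42 and 56) fall in the double-blind period, while V2 and V7 close the single-blind placebo run-in and washout.

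**2. Exposure**

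The Synopsis gives 2 weeks run-in + 8 weeks double-blind + 1 week washout = 11 weeks. Treatment durations are 6 weeks V117957 + 5 weeks placebo = 11 weeks. If the 5 placebo weeks include run-in and washout, double-blind placebo is 5 - 2 - 1 = 2 weeks, against 6 weeks of V117957. That would be roughly one double-blind placebo clinic visit in four per woman. The treatment sequences are not given in the available text, so the number on placebo at each visit is not known. On this reading 3 of the 5 placebo weeks are single-blind, so it matters whether V2 and V7 are pooled with double-blind placebo.

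**3. The plan's own figure**

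No figure is stated for safety. The sample-size statement supplies the number of pairs: 38 completers, difference 0.5, SD of differences 1.4, one-sided 10%. Noncentrality = (0.5/1.4) × √38 = 2.20 with 37 df, giving power 0.815 against the stated 81%. It reproduces, and nothing here changes it.

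**4. What pairing could add**

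Assumptions: 38 women with one value per treatment, common SD σ, within-subject correlation r. The documents give neither σ nor r for any safety measure.

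- Paired 90% CI half-width = t(0.95; 37) × σ√(2(1 - r)/38).
- Same two columns treated as independent: t(0.95; 74) × σ√(2/38) = 0.382σ.

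| r | Paired half-width | Unpaired / paired |
|---|---|---|
| 0.3 | 0.324σ | 0.382/0.324 = 1.18 |
| 0.5 | 0.274σ | 0.382/0.274 = 1.39 |
| 0.7 | 0.212σ | 0.382/0.212 = 1.80 |

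The gain is therefore about 1.2 to 1.8 times. Averaging several V117957 visits, or adjusting for period in an unbalanced schedule, would change these values.

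**The case against.** The strongest reply is that this is a Phase 1b study of about 44 women, sized on bladder pain, with no comparative safety hypothesis. Descriptive safety reporting is usual in such a study, and many uncontrolled intervals would themselves invite chance findings. This stands against requiring a model for every laboratory, vital-sign and ECG parameter. It does not explain why a named numeric endpoint has no summary by treatment.

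The available text is also at summary level and partly redacted, and section 1.3 refers to the statistical analysis plan for exclusions from the analysis sets. More detail may exist elsewhere, so the point holds for the text provided.

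A reader might also infer more than the documents support:

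- *That laboratory values and vital signs get no treatment comparison.* They do get a descriptive one, by treatment and time point. Only the within-subject difference is missing.
- *That adverse events are handled better.* They have incidence by treatment group and no paired contrast either.
- *That each table row compares different women.* This is so if time point means study visit. If it means time within a treatment period, the same woman can appear in both columns. The term is not defined.
- *That the planned tables are 1.6 to 2.8 times less precise.* Those ratios arise from setting 38 pairs (SE 0.192σ to 0.126σ for r = 0.3 to 0.7) against a single visit row of 44 women, split 22 v 22 (√(1/22 + 1/22) = 0.302σ) or 11 v 33 (√(1/11 + 1/33) = 0.348σ). The splits are assumed, no inference from a single row is planned, and the comparison is not like for like.

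Carryover is a further limit. The schema shows no washout within the 8 double-blind weeks, so a placebo visit that follows V117957 may not be clean. That calls for caution in reading a within-subject difference, and it affects an unpaired table as well.

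**Conclusion.** The point holds in a limited form. In the text provided, three named safety endpoints that are collected throughout the study (ESS, ECG and C-SSRS) are listed without any summary by treatment. Laboratory values and vital signs have a summary by treatment but no within-subject difference. This is a missed use of the crossover and a gap against the stated safety objective. It does not make any planned analysis invalid, and it leaves sample size and power unchanged.

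The first part rests on the text alone and needs no numerical assumption. The value of pairing, about 1.2 to 1.8 times in interval width, rests on an assumed correlation of 0.3 to 0.7 and one value per treatment in 38 women. The inferred split of 6 to 2 double-blind weeks supports showing single-blind placebo separately, but the conclusion does not depend on it.

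**What to change.** In section 1.4.3:

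1. State that ESS total score, ECG parameters and C-SSRS responses will be summarized by the treatment being taken at the time of assessment, with the single-blind placebo visits (V2 and V7) shown separately.
2. For ESS total score, and as descriptive support for key ECG and vital-sign measures named in advance, report the within-subject V117957 minus placebo difference over the double-blind visits (V3 to V6) with a 90% CI. Use the model structure of section 1.4.1: treatment, period and sequence as fixed effects, and subject within sequence as random.
3. Label these contrasts descriptive and without multiplicity control, and note that carryover is possible because the schema shows no washout within the double-blind period.
4. Define *time point* and *period* for the safety tables. Keep the listings and the planned laboratory and vital-sign summaries.

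The cost is wording, some programming and a few extra tables, with no new visits, procedures or subjects. The downside is a small set of unadjusted intervals in which a chance difference may appear; naming the measures beforehand and labelling them descriptive limits this.
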